#### **Wake EEG recordings and neurobehavioral assessments**

The subjects will be instructed to relax without falling asleep and to fixate a point on the wall for 3 min while breathing at a stable pace and then to close their eyes for 3 min while breathing normally. During the recording, the subjects will be under constant supervision. Spectral analysis of wake EEG will be performed using specially designed software (PRANA, PhiTools, Strasbourg, France) in the delta, theta, alpha, sigma, beta and gamma bands. After artifact removal, a spectral analysis, using a Fast Fourier Transformation, will be computed for 2-sec epochs for the two EEG derivations with a resolution of 0.5 Hz. The data will then be averaged for the first and the second 3-min periods in different frequency ranges, e.g. from low delta (0.5-2 Hz) to gamma (>30 Hz). Measures derived from the wake EEG include the alpha-slow wave index (ASI) defined as the ratio of EEG power in the alpha band over sum of power in the theta and delta bands) and the EEG power in the beta range of the wake EEG, a marker of alertness largely distinct from the ASI. Subjective ratings of sleepiness (Stanford Sleepiness Score), mood and vigor (VAS), Positive Affect Negative Affect Scale), hunger, appetite for various food categories, will be obtained daily in the mid to late morning, mid afternoon and evening, together with the wake EEG. Subjective sleep quality and quantity will be obtained using the Karolinska sleepiness scale every morning upon awakening. Neurobehavioral function will be measured using 5-min psychomotor vigilance test (PVT).

#### *Multiple sleep latency test*

The gold standard to evaluate physiological sleepiness is the multiple sleep latency test (MSLT), a series of five nap opportunities presented at 2-hour intervals beginning approximately 2 hours after initial (morning) awakening. Individuals undergoing an MSLT are instructed to allow themselves to fall asleep during the nap. Subjects are tested under standardized conditions in their street clothes and are not permitted to remain in bed between nap test sessions. Electrophysiological measures (EEG, EOG, EMG) needed to detect sleep onset and score sleep stages are recorded during nap opportunities. Unequivocal sleep is an epoch of stage 2, 3, or 4 or rapid eye movement sleep (REM) sleep. Sleep latency is defined as the elapsed time from the start of the test to the first 30-sec epoch scored as sleep.

#### **2-hour oral glucose tolerance test (OGTT)**

The 2-hour OGTT will be used as a screening test for assessment of glucose tolerance status (normal, impaired glucose tolerance and diabetes) as well as an outcome measure. After an overnight 12-hour fast, an intravenous catheter will be placed into an antecubital vein for blood drawing. Baseline samples of glucose, insulin and C-peptide will be taken at -15 and 0 minutes. At time 0, 75 g of glucose is administered orally, and blood samples are collected for the measurement of glucose, insulin, and C-peptide concentrations at 30, 60, 90 and 120 min. Diagnostic measures include baseline and 2-hour glucose concentrations. Normal glucose tolerance, impaired glucose tolerance and type 2 diabetes will be defined based upon the plasma glucose concentration at 2 h using the criteria of the Expert Committee on the Diagnosis and Classification of Diabetes Mellitus of the American Diabetes Association. Specifically, a diagnosis of normal glucose tolerance, impaired glucose tolerance, or diabetes is assigned if the glucose level at 2 h is less than 140 mg/dl, between 140 – 200 mg/dl, or 200 mg/dl or more, respectively.

**Frequently sampled intravenous glucose tolerance test (fsIVGTT)**

The fsIVGTT will be used to estimate insulin sensitivity by the Bergman minimal model as well as the adequacy of the first phase insulin secretory response to an intravenous glucose bolus. Starting at 09:00 after an overnight fast, blood samples (1 ml) will be drawn every 5 min for 10 min (3 baseline samples), at which time 0.3 g/kg glucose will be administered as an intravenous bolus. Blood samples will be taken at 2, 3, 4, 5, 6, 8, 10, 12, 15, 19, 21, 22, 24, 26, 28, 30, 40, 50, 60, 70, 90, 100, 120, 140, 180, 210 and 240 min. At time 20 min, intravenous insulin (0.02 U/kg) will be administered. The following summary measures will be derived: baseline insulin concentration, first phase area under the insulin curve from 0 min to 19 min; acute insulin response to glucose (AIRg) from 0 min to 10 min; insulin response expressed as a percentage of baseline insulin level; glucose tolerance index (Kg), insulin sensitivity index (SIi), and glucose effectiveness at the basal insulin level (SG). The so-called disposition index (DI), i.e., AIRg x SIi, is calculated to express beta-cell function in relation to the degree of insulin resistance.

**Blood sampling and hormonal assays**

24-hour blood sampling will be performed at 15-minute intervals for 2.5 hours after each standardized meal (served at 9:00, 14:00 and 19:00) and for 2 hours after scheduled bedtime, and at 30-minute intervals at all other times for measurements of glucose, C-peptide, insulin, GH, cortisol, leptin, CRP (assayed every 4 hours), estrogen, testosterone, progesterone, acylated and non-acylated ghrelin. Blood samples will be obtained every hour for catecholamines. FFA will be obtained right before each meal and 1 hour and 2 hours after. FFA will also be obtained every hour during the night. During periods of frequent blood sampling, a sterile heparin-lock catheter will be inserted in the forearm and the line will be kept patent by a slow drip (10 cc/hr) of heparinized saline (750 IU/dl). All blood samples will be collected through the lateral arm of a three-way stopcock. During waking hours blood samples will be collected at the bedside. During sleep hours the intravenous line will be extended and fed through a light-tight port in the wall, thus allowing disturbance-free blood drawing from a next-door sampling room. The total amount of blood withdrawn during each of the proposed studies will not exceed 500 ml. Blood samples will be centrifuged immediately at 4°C and plasma will be frozen and stored at -80°C until assay. For each hormonal variable, all samples obtained from the same subject will be measured in the same assay. C-peptide, Insulin, GH and cortisol, leptin, CRP (assayed every 4 hours), estrogen, testosterone and progesterone will be measured by chemiluminescence assays using the Immulite Immunochemistry System (Diagnostic Products Corporation). Results with the DPC Immulite, as assessed by our previous experience, or according to College of American Pathologists surveys reporting use of the instrument in clinical lab settings, demonstrate sensitivity, accuracy and reproducibility that meet all the requirements of the proposed research. Ghrelin levels will be measured by RIA (Linco Research, Inc., St. Louis, MO) kit for acylated and total ghrelin. Sensitivity is 10 pg/mL.

**Plasma catecholamines** (q60min) will be measured using the ESA Coulechem Md 5001 instrument. In this method, the catechols are first partially purified from plasma by absorption to a silica powder. Norepinephrine (NE) and epinephrine (E) are separated upon emergence from an HPLC column and quantified in a partially purified state on the basis of a reversible oxidation reduction as each catecholamine passes across a set of electrodes. The precision (CV's) of the ESA procedure, at physiologic catechol levels (NE >100 pg/ml, E 20 - 60 pg/ml) has been found to be, 6.0 - 1.8 and 4.8 - 8.0% respectively for NE and E intra- or inter-assay. Our group has recently published 24-h profiles of catecholamine levels, showing exquisite delineation of meal responses and age effects.

**Triglycerides** will be measured using a Serum Triglyceride Determination kit (Sigma-Aldrich, Inc.).

FFA concentrations will be assayed with enzymatic colorimetric kits (Wako Chemicals USA, Richmond, VA).

**Hormonal assays for the GnRHa Test**

Estradiol will be assayed by a modification of a Pantex kit method after extraction of plasma with a sensitivity of 2.8 pg/ml and precision of 11%. Steroid intermediates (17-hydroxyprogesterone and

androstenedione) will be measured after extraction, purification by thin-layer chromatography, and RIA. These methods are sensitive to approximately 25 ng/dl and have a precision averaging 13%. Total testosterone will be measured by a nonchromatographic method using a Diagnostics Products kit with a sensitivity of <20 ng/ml and a precision of 11%. Free testosterone will be computed from a competitive protein binding analysis with a sensitivity of 3 pg/ml, precision of 13%.

#### **Body composition and body fat distribution**

Waist circumference and waist/hip ratio will be measured. Bioimpedance will be performed. Body composition and fat distribution will be assessed by abdominal MRI (112).

#### **Subcutaneous fat biopsy (to be performed by PI in the GCRC)**

The abdominal area adjacent to the umbilicus is prepped with betadine solution. An area approximately 12 to 15 cm in diameter is prepped and allowed to air dry. Anesthetic agent is pre-mixed by removing 5cc of 1% plain lidocaine from its bottle and replacing the volume removed with 5cc of 8.4% sodium bicarbonate solution. Lidocaine field block is performed using 10cc of the premixed lidocaine/bicarbonate mixture. The area is allowed to become anesthetized for approximately 10 min after the field block, during which time it is covered with sterile 4x4. An incision approximately 0.5cm long is made parallel to the patients' waistline in the central portion of the field-blocked area, through the dermis and into the subcutaneous adipose tissue. Pre-filled 60cc syringes containing 10cc normal saline are used to aspirate the adipose tissue using a 13 gauge 3-inch hypodermic needle. Gentle aspiration back/forth motion is used to aspirate the adipose tissue. This is subcutaneous biopsy and the proper angle is approx parallel to the skin and extending up 15 degrees from the plane of the abdomen. Up to 5 syringes are used per abdominal site, depending on the sample size needed for the study. Steri-strips are used to close the wound site and folded 4x4's are placed over the strips and secured using Elastoplast. Direct pressure is applied to the wound for 5-10 minutes immediately afterwards. Ice packs are given to the patient to apply to the area after the procedure.

#### **Assessments in adipocytes (performed by [name], PI – Project 4)**

Adipocyte preparation: Adipose sample is weighed and placed in DMEM + 1% BSA (Type V, Sigma #A7888) + 5 mM glucose + 10 mM Hepes (pH 7.4) (DMEM\*). Collagenase stock solution is prepared using 3.5 ml of DMEM\*/gram of fat) and 1 mg/ml collagenase (type II, Sigma #C6885). Adipose tissue is minced with a double pair of scissors, approximately 100-150 strokes. Samples are then incubated for 5 min at 37oC. Cells are transferred to new vials containing collagenase solution and incubated for a further 60-75 min at 37oC, swirling vials every 5 min. Cells are transferred to 15 ml conical tubes containing 10 ml of DMEM\*. Adipocytes are washed 3X using centrifugal centrifugation (120 rpm) using 10 mls of DMEM\*/wash. After final wash, excess media is completely removed and packed cells are used for in vitro assays.

Signaling Assays: 100 ml of packed cells are transferred into 1.5 ml epindorf tubes. 100 ml of DMEM\* containing 2X final concentration of insulin (0-20nM) is added to the tubes. Cells are gently vortexed and incubated at 37oC for 10 min. Cells are then washed 3X in DMEM (no BSA) and lysed by addition of 200 ml of 2X Laemli buffer. All samples are boiled for 2 min, and then spun at 10,000 rpm for 10 min, RT. Samples are separated by SDS-PAGE, transferred to nitrocellulose for immunoblotting with appropriate antibodies.

Metabolic Assays: 200 ml of packed cells are transferred in triplicate into 1.5 ml epindorf tubes. 200 ml of DMEM\* containing 2 mCi 14C-glucose, -/+ 10 nM insulin is added to appropriated tubes. Reactions are incubated at 37oC for 30 min, and vortexed every 5 min. At the end of the assay, half of the cells are transferred to glass test tubes and glycogen isolated using ethanol precipitation. Glycogen pellets are dried overnight, solubilized in 1 ml of water, and 14C-glucose incorporation into glycogen is determined by liquid scintillation counting. The other half of the reaction is transferred to 7 ml scintillation vials containing 900 ul of PBS and 4 ml of Betafluor is added to each vial. Vials are capped and shaken vigorously to extract the

lipids. The next day, the top 3 ml from each vial are transferred to new vials and radioactivity incorporated is determined by liquid scintillation counting.

**Adipocyte culture:** Primary adipocytes are resuspended in DMEM +2% FBS in a 1:1 ratio of cells to media and allowed to recover at 37°C, 6% CO2 for 30 minutes. After recovery, cells are added to Matrigel Basement Membrane Matrix in a 2:3 ratio, and 250  $\mu$ l of cell/Matrigel suspension are plated per well on a 12 well plate. Plates are then placed at 37°C for 30 minutes to allow the matrigel to polymerize, after which 500  $\mu$ l of DMEM +2% FBS are added per well.

### **Cardiovascular measures**

Systolic and diastolic arterial blood pressure will be measured at 15-min intervals during the daytime from the non-dominant arm using ambulatory monitoring equipment (Accutracker II, Suntech Medical Instruments). Resting EKG recordings (Nihon Kohden) using two thoracic electrodes will be used to record heart rate and HRV. Time domain measures of HRV including SDNN, NN50, pNN50, r(iNN) will be calculated using ectopy and artifact free 5-min bins. Spectral power estimated in the high frequency band (HF component; 0.15 – 0.40 Hz) will be used as a measure of parasympathetic activity. Other measures of cardiac sympathovagal balance will include spectral power in the low frequency band (LF component; 0.04 – 0.14 Hz) and the LF/HF ratio. The total power in the 0.04 – 0.40 Hz band will be used to normalize absolute LF and HF values.

### **Measures of energy expenditure**

We will use accelerometer-based assessments (Actical, Mini-Mitter Co. Inc, Bend, OR) to monitor the stability of activity levels in each study condition during the entire study period. The Actical is a small lightweight device (17g; 28 x 27 x 10 mm) sensitive to omni-axial accelerations, which are sampled at 32 Hz, converted to activity counts, and integrated over 1-minute epochs. The participants will wear the Actical around the clock (except when bathing) attached to an elastic waist band above their right iliac crest.

### **Metabolomics**

Blood and urine will be collected, temporarily stored at – 80°C, and sent to the Metabolomics Laboratory at Duke University. Measurement of analytes in a targeted fashion is achieved by addition of known quantities of stable isotope-labeled internal standards to an array of sample types, including extracts of cells in culture, as well as bodily fluids and tissue extracts of model organisms and human subjects. The laboratory has also recently obtained the new Waters Acquity Ultra Performance LC (UPLC)™ and LCT Premier™ LC/MS systems. The enhanced chromatographic peak capacity and sensitivity of the UPLC, coupled with the high resolution and mass accuracy of the LCT Premier, allows for “unbiased” analysis of as many as 5000 individual metabolites in a single specimen. Although the identity of most of the analytes is unknown when using the LC/MS instrument, the Waters MarkerLynx™ statistical analysis software can be used to define principal components (groups of analytes) that discriminate different samples (e.g., samples taken before and after a period of drug therapy or before and after an intervention such as continuous positive airway pressure (CPAP)). Once a set of metabolites has been shown to correlate with functional states, the identity of the individual analytes can be determined by additional chemical and MS-based analyses.

**E. HUMAN SUBJECTS RESEARCH****1. Risks to the Subjects****a. Human Subjects Involvement and Characteristics**

- Study subjects will include women with PCOS. Subjects will be between 18 and 40 years of age.
- Women > 40 years of age will not be recruited to avoid the confounding variable of age related alterations upon ovarian steroidogenesis. It is anticipated that the majority of subjects will be aged between 25 and 35 years.
- Women with nonclassic 21-hydroxylase deficiency congenital adrenal hyperplasia will be identified by and AM 17-hydroxyprogesterone blood level. In cases where there is question, subjects will be advised to undergo an adrenocorticotropin stimulation test. Women with this disorder will be excluded from further study as will those with Cushing's syndrome. There will be no exclusion criteria based upon race, but subjects with systemic illnesses, including heart, renal, liver, or malignant disease will be excluded. Individuals with known peanut allergy or allergies to medications used in this study will be excluded.
- Pregnancy status will be checked. Pregnant women will be excluded from study.
- With the exception of children, the proposed studies will *not* include special classes of subjects. Specifically, studies will *not* include fetuses, neonates, pregnant women, prisoners, institutionalized individuals.
- Individuals known to be diabetic will not be enrolled in studies; those who prove to be diabetic upon screening will discontinue participation in the protocols.
- Subjects with hypertension (systolic > 140 mmHg and/or diastolic > 90mmHg) will be included only if well-controlled on stable medication with either ACE inhibitors or diuretics. Subjects on beta-blockers will be excluded as these drugs affect both insulin sensitivity and sleep.

**b. Source of Materials**

- Research materials to be obtained from study subjects includes blood and urine samples for hormonal and biochemical measures. Blood samples will be collected for research purposes.
- Fat cells from the subcutaneous tissue will be obtained by biopsy procedure.
- Existing records will not be incorporated as part of the study files.

**c. Potential Risks**

- The clinical procedures involve a minimal discomfort associated with venipuncture. There might be slight bruising at the site that will recover in a short period of time. There is also slight risk of inflammation of the vein or infection. However, our nurses who perform these procedures are highly trained and thus these risks are minimal. The amount of blood withdrawn is minimized to prevent significant blood loss. Baseline hematocrit will be measured in all subjects to ensure that this risk is not excessive.
- There are no known direct or permanent side effects from a single injection of either diagnostic leuprolide (10mcg/kg body wt) or depot leuprolide (11.25mg). In women the changes in hormones may change the timing or pattern of the menstrual cycle during which it is given, or cause transient water retention, breast tenderness, or mood changes. Occasional patients have reported headache, GI upset, back pain, mild fever, or increased libido after a single dose of leuprolide. Swelling and tenderness at the injection site may develop. The safety of leuprolide during pregnancy and risk of treatment to an unborn fetus is unknown. Women will be instructed to use an effective non-hormonal form of contraception, such as condom with spermicidal foam or IUD.

- Insulin. Insulin administered as part of the fslVTT will raise plasma insulin levels transiently, but hypoglycemia is rare given that the insulin is administered only after a glucose bolus has been given as part of the procedure.
- Micronized progesterone will not be given to individuals with known peanut allergy since the capsules are known to contain peanut oil. Likewise, this medication will not be given to women with undiagnosed vaginal bleeding or a history of deep vein thrombosis. Patients may experience headache, breast tenderness, bloating, or depression as a result of use of this medication. Patients will be informed of these risks and all efforts will be taken to minimize them.
- Micronized estrogen will not be given to individuals with known peanut allergy since the capsules are known to contain peanut oil. Likewise, this medication will not be given to women with undiagnosed vaginal bleeding or a history of deep vein thrombosis. Patients may experience nausea, headache, breast tenderness, or bloating as a result of use of this medication. Patients will be informed of these risks and all efforts will be taken to minimize them.
- The GCRC nurses who perform these procedures are highly trained and thus the risks directly associated with intravenous puncture and blood withdrawal described above are minimal. For those subjects randomized to take pioglitazone, monitoring of hepatic function will be performed as described above. Subjects may choose not to participate in the study, and may discontinue the study at any time point. Conventional diagnostic and therapeutic modalities will be made available to all subjects where appropriate. In the event of physical injury resulting from this research, the University of Chicago Hospitals will provide emergency care at no cost to the subject, if such care is necessary. The University of Chicago Hospitals will also provide non-emergency care, but the Medical Center assumes no responsibility to pay for such care or to provide financial compensation. Confidentiality is always respected. Specimens are logged by number according to routine practices of the institution. Data collected are included in the patients' charts and results of the studies are made available to patients, their legal guardian, and their referring physicians. Samples are not available to any investigators other than those listed herein.

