**Figure D1-1. Schematic of overall study design for Specific Aims 1 - 3.**

hyperplasia, Cushing syndrome, hypothyroidism, or significant elevations in serum prolactin. Thus, all subjects will meet the so-called NIH criteria for PCOS (113) as well as the Rotterdam criteria for PCOS (114). For at least 2 months before the study, all subjects must not take steroid preparations (including oral contraceptives), medications known to alter insulin secretion and/or action, or medications known to influence sleep. All studies will be conducted in the follicular phase of the menstrual cycle (days 1 – 7) or after 2 or months of amenorrhea. A negative pregnancy test will be required prior to all testing procedures. Subjects who are known to be diabetic will be excluded; those who prove to be diabetic on screening will not continue in subsequent protocols. Subjects with hypertension (systolic > 140 mmHg and/or diastolic > 90 mmHg) will be included only if well-controlled on stable medication with either ACE inhibitors or diuretics. Subjects on beta-blockers will be excluded as these drugs affect both insulin sensitivity and sleep. Subjects must have regular life styles (no shift work, no travel across time zones within 4 weeks of study), and habitual bedtimes. Other exclusion criteria will be: habitual alcohol use of more than 2 drinks per day and excessive caffeine intake of more than 300 mg per day.

Table D1. Summary Grid of Tests by Specific Aim.	SPECIFIC AIM 1		SPECIFIC AIM 2		SPECIFIC AIM 3
	Obese PCOS OSA Negative	Obese PCOS OSA Positive	Obese PCOS OSA Positive		Obese PCOS OSA Positive
			Depot Leuprolide	Depot Leuprolide	
			Estrogen plus Placebo	Progesterone plus Placebo	CPAP
SAMPLE SIZE	23	23	20	20	20
Oral glucose tolerance test (OGTT)	2	2	2	2	2
Frequently sampled IVGTT (fsIVGTT)	2	2	2	2	1
Androgen levels (total, free T, et al.)	1	1	2	2	2
Estradiol, Estrone, Progesterone	1	1	2	2	2
Gonadotropins (LH, FSH)	2	2	2	2	2
Metabolomics profile (blood, urine)	2	2	2	2	2
24 hr hormonal profiles (including Cortisol and Catecholamines)	2	2	2	2	1
Plasma catecholamines	2	2	2	2	2
Abdominal MRI, Bioimpedance	2	2	2	2	2
Adipose tissue biopsy	2	2	2	2	2
Serum for adiponectin	2	2	2	2	2
Sleep and Activity Assessment	2	2	2	2	2
Sleep questionnaires	2	2	2	2	2
Wrist activity monitoring	2	2	2	2	2
Multiple sleep latency test (MSLT)	2	2	2	2	2
Sleep recording/Polysomnography	1	1	1	1	1
Wake EEG/Neurobehav. assessments	2	2	2	2	2

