### **Screening and Specific Aim 1 Procedures, cont'd.**

**Figure D2-1. Schematic of Screening Visit. Clock time is shown along horizontal axis.**

Subjects will receive instructions on the logs/scales and practice the psychomotor vigilance test (PVT) to be used in the study. Subjects will also complete screening questionnaires including the Pittsburgh Sleep Quality Index, Berlin Questionnaire, Epworth Sleepiness Scale, Center for Epidemiologic Studies-Depression (CES-D) scale, Functional Outcome of Sleep Questionnaire (FOSQ), and the Beck Scale. An overnight full polysomnography will be performed to differentiate the subjects with from those without OSA.

For all protocols in this SCOR application the presence of OSA will be defined by an apnea-hypopnea index (AHI) of greater than 15 events per hour sleep (AHI > 15); the absence of OSA will require an AHI of less than 5 events per hour sleep (AHI < 5). This criterion is consistent with current standards and ensures that subjects with periodic limb movement disorder (PLM arousal index > 1) are excluded from study.

On the day following the full polysomnography, a 2 hr OGTT, a complete history and physical examination, routine laboratory tests (CBC, electrolytes, renal, liver function tests) and an EKG will be performed. This screening visit will also serve to familiarize the subject with the study environment and the experimental procedures.

[figure not shown]
Once the Screening Visit has been completed if the subject is deemed eligible to continue, they will be instructed on completing one week of continuous wrist actigraphy at home; subjects will be asked to maintain a standardized schedule of bedtimes and mealtimes designed in accordance with their usual habits. They will be asked not to deviate from this schedule by more than 30 minutes. During this pre-study period, subjects will also be asked to fill out a daily log of sleep and meal times. Subjects who have shown poor compliance will be given the option to repeat the week of ambulatory recordings. If compliance remains poor, subjects will be excluded from further study.

After the screening visit and completion of the ambulatory recordings, the subsequent experimental procedures depicted in Figure D2-2 and described below will occur.

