**At 15:50, a GnRH agonist test will be performed, as depicted in FIGURE D2-3 below.**

At 15:50, a 15cc blood sample for LH, FSH, estradiol, estrone, total and free testosterone, progesterone, 17-hydroxyprogesterone, and androstenedione will be obtained. At 15:59, a 5 cc blood sample will be taken for LH and FSH. At 16:00, leuprolide acetate 10 µg/kg will be given as a single subcutaneous injection. At 16:30, 17:00 and 20:00, 5 cc samples will be obtained for LH and FSH. A 15 cc sample will be obtained for estradiol, estrone, total and free testosterone, progesterone, 17-hydroxyprogesterone, and androstenedione after 16, 20, 24 hours GnRHa administration, i.e. at 8:00, 12:00 and 16:00.

As depicted in Figure D1-1, it is at this point that subjects will have completed the Screening and Specific Aim 1 Procedures. Details of procedures for subjects randomized into Specific Aim 2 or Specific Aim 3 are provided below.

### D3. Detail of methods pertaining to Specific Aims 2 and 3

The PCOS women with OSA studied in Aim 1 plus additionally enrolled PCOS women with OSA (for a total of 60 subjects) will be randomized in a ratio of 2:1 to participate in Aim 2 (n=40) or Aim 3 (n=20). Block randomization will be performed using computer-generated random numbers. The primary outcomes measure for Aim 2 is the AHI difference pre- and post-interventions, as detail in Section D3; the primary outcomes measure for Aim 3 is the change in 24 hr cortisol concentration pre- vs post-CPAP

Subjects randomized to Specific Aim 2 will have suppression of endogenous LH secretion, and thus ovarian sex-steroid production, by administration of a single intramuscular dose (11.25 mg) of the GnRH agonist depot leuprolide. Leuprolide is a synthetic nonapeptide analog of naturally occurring gonadotropin-releasing hormone (GnRH). The analog possesses greater potency than the natural hormone. When the depot form of leuprolide is administered at a dose of 11.25 mg, there is prolonged (3 month) suppression of pituitary gonadotropin levels and ovarian steroid levels as documented in the literature (115) and exemplified in Preliminary Studies. Six-weeks after administration, subjects will return to the GCRC for repeated evaluation, identical to that conducted at Baseline under Specific Aim 1.

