**b. Protection Against Risk**

The following will be specifically instituted to protect human subjects from research risks:

- subjects with systemic illnesses, including heart, renal, liver, or malignant disease will be excluded. Pregnant women, women with known peanut allergy or allergy to any planned study medication will be excluded.
- The nature of the research project will be described in detail to the subjects and written summaries, in lay terms, of the research proposed will be provided for review. Written informed consent will be obtained by the P.I. from the subjects and/or parent/legal guardian where appropriate. The protocols and consent forms have been approved by the Institutional Review Board at the University of Chicago.
- The amount of blood withdrawn will be minimized to prevent significant blood loss.
- Baseline hematocrit will be measured in all subjects to ensure that this risk is not excessive. A cooling or heating apparatus will be available in the event that local venipuncture site swelling develops.
- Women will be instructed to use an effective non-hormonal form of contraception, such as condom with spermicidal foam or IUD for studies that will alter sex-steroid levels.

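### Two bars on both Aim 2 hormones, prior deep vein thrombosis and undiagnosed vaginal bleeding, are not carried into the exclusion criteria that govern randomisation and the leuprolide depot

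*Combined protocol and SAP*

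**What the plan says.** Section E.1.c takes the two Aim 2 hormones in turn. Each is withheld in known peanut allergy, and for each the same further sentence follows: "Likewise, this medication will not be given to women with undiagnosed vaginal bleeding or a history of deep vein thrombosis".

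Exclusions are set out in three places.

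- Section E.1.a: "Individuals with known peanut allergy or allergies to medications used in this study will be excluded", and "subjects with systemic illnesses, including heart, renal, liver, or malignant disease will be excluded".
- Section E.2.b: the same systemic-illness rule, then "Pregnant women, women with known peanut allergy or allergy to any planned study medication will be excluded".
- Section D1: diabetes, uncontrolled hypertension, beta-blockers, irregular schedules, alcohol and caffeine, besides the conditions ruled out in diagnosing PCOS. It also has a timing rule: "All studies will be conducted in the follicular phase of the menstrual cycle", or after a spell of amenorrhea.

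At the screening visit (section D2), "a complete history and physical examination, routine laboratory tests (CBC, electrolytes, renal, liver function tests) and an EKG will be performed". Women go on only "if the subject is deemed eligible to continue".

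Under the D3 methods section, OSA-positive women are randomised 2:1 to Aim 2 or Aim 3. Those in Aim 2 receive a single 11.25 mg dose of depot leuprolide, after which "there is prolonged (3 month) suppression of pituitary gonadotropin levels and ovarian steroid levels". At six weeks (T2) they return for an evaluation identical to baseline. Only then are they randomised to estradiol or progesterone for six weeks.

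**The concern.** The plan applies two sets of rules to the same women and they do not match. One says who may take the study hormones; the other says who may enter. A woman with a past deep vein thrombosis or unexplained vaginal bleeding fails the first and passes the second. Both Aim 2 arms carry the same bars, so she cannot be moved to the other arm.

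At stake is exposure that serves her no purpose: an injection that cannot be withdrawn, some months of ovarian suppression, and a second admission that repeats the fat biopsy, the intravenous glucose tolerance test and the 24-hour blood sampling. The trial also spends a recruit who cannot supply the on-treatment T3 value that the Aim 2 primary comparison needs.

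**Working it through.** No arithmetic applies; the check sets one text against another.

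**Step 1. Trace each bar from E.1.c into the exclusion lists.**

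| Bar on both hormones (E.1.c) | D1 | E.1.a | E.2.b |
|---|---|---|---|
| Known peanut allergy | not named | excluded | excluded |
| Undiagnosed vaginal bleeding | not named | not named | not named |
| History of deep vein thrombosis | not named | not named | not named |

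One bar of three is carried over. The OSA and limb-movement criteria in D2 and in the polysomnography methods (D5) name neither of the other two.

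**Step 2. Does another criterion cover them?** The nearest is systemic illness. Its examples are heart, renal, liver and malignant disease. A resolved thrombosis or unexplained bleeding is not clearly among these, although the list is introduced as non-exhaustive. The cycle-timing rule in D1 would draw attention to bleeding but not to a past thrombosis.

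**Step 3. Does the screening visit close the gap?** The complete history comes before the 2:1 randomisation and may reveal either condition. But the decision that a woman is eligible to continue has to be made against the stated criteria, and those omit both conditions. No rule turns a positive answer into ineligibility for Aim 2.

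**Step 4. Follow an affected woman through the sequence.**

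1. Screening: no stated criterion excludes her.
2. 2:1 randomisation: she may be assigned to Aim 2.
3. Depot leuprolide: nothing in the stated criteria prevents it.
4. T2 at week 6: full repeat evaluation.
5. Estradiol or progesterone: both forbidden under E.1.c.

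The documents do not say when the E.1.c bar is checked. A repeat history at T2 is neither required nor ruled out.

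**Step 5. What does this do to the analysis?** No planned primary analysis compares Aim 2 with Aim 3. Aim 2 compares the T3 minus T1 change in AHI between the two hormone arms, and Aim 3 is a paired test within the CPAP group. The randomisation that supports the Aim 2 comparison happens after T2. A woman found barred at or before T2 therefore belongs to neither arm. Her T2 hormone levels could still enter the paired T2-versus-T1 comparison.

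**The case against.** The strongest reply is that E.1.c already prevents the dangerous event. A reader might infer from the mismatch that the plan lets women with a past thrombosis take estrogen. It does not; dosing is explicitly forbidden. That part of the reply stands in full.

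A reader might also infer a loss from the randomised arms of 20, with reduced power or bias. The documents do not support that. Arm assignment follows T2, the bars are identical in both arms, and section D4 expects that additional subjects may be recruited to replace drop-outs.

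It can also be said that harm requires staff to learn of a thrombosis at screening, know that both drugs are barred, and give the depot anyway. That is improbable where the history is volunteered and acted on. But the plan relies on the investigator to make that link unprompted, having written it down as an exclusion for peanut allergy. Nothing in the documents explains why one bar was carried over and two were not.

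For bleeding, the reply has more force. It can begin at any time, so a bar at dosing is a sensible place for it, and a screening rule cannot catch bleeding that starts later. This argues for asking at both points rather than against asking at screening.

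Finally, E.1.c reports no known direct or permanent side effects of a single leuprolide injection. It does list transient effects such as water retention, mood change and headache, so the exposure is small but not nil.

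**Conclusion.** The mismatch is real and can be verified from the text: two of the three bars on both Aim 2 hormones appear in none of the exclusion lists. Followed literally, the eligibility rules admit a woman to Aim 2, the depot and the T2 admission with no treatment arm open to her.

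The consequence is minor. It is a matter of participant protection and wasted recruitment, not of bias, power or validity. That judgement assumes that the E.1.c bar is enforced no later than T2, before arm assignment; the documents imply that no barred woman is dosed but do not state when the check is made. The documents give no prevalence for either condition, so the number of women affected cannot be estimated, and the point does not depend on it.

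**What to change.** In sections D1, E.1.a and E.2.b, add for women entering the 2:1 Aim 2/Aim 3 randomisation:

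- History of deep vein thrombosis: exclusion.
- Undiagnosed vaginal bleeding: deferral until evaluated and explained, after which the woman may enter. Section E.1.c already makes conventional diagnostic care available.

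Check both at the D2 screening history, before the 2:1 randomisation and so before the depot. Ask both again at T2, before the estradiol/progesterone randomisation, because bleeding can begin in the interval. The T2 check can be done blind since the bars are the same for both drugs.

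The cost is two history questions at each of two visits already planned. The downside is that a few women who could have used CPAP in Aim 3, for which the documents state no such bar, are excluded (thrombosis) or delayed (bleeding). Applying the rule before the 2:1 randomisation makes this unavoidable, because assignment to Aim 2 or Aim 3 is not yet known. These women may still complete Aim 1.
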